4.1. Inclusion Criteria

Patients must meet all of the following inclusion criteria to be eligible for enrollment into the study:

1. Diagnosis of locally advanced or metastatic HCC, obtained by histology/cytology (on a prior tumor biopsy) or by imaging (acceptable imaging modalities include triphasic contrast-enhanced helical computerized tomography [CT], triphasic dynamic contrast-enhanced magnetic resonance imaging [MRI] and contrast-enhanced ultrasonography) with serum α -fetoprotein (AFP) ≥ 400 ng/mL.
2. All patients must provide at least 1 archival tumor specimen. If archival tumor specimen is no longer available, *de novo* tumor biopsy will be required during screening.
3. HCC not amenable to local therapy.
4. Measurable disease according to RECIST v. 1.1.
5. Child-Pugh Class A disease (see [Appendix 2](#)). Score for hepatic encephalopathy must be 1; ascites score must be ≤ 2 .
6. Barcelona Clinic Liver Cancer (BCLC) stage B or C disease. Stage B disease must be unresectable, not amenable to local therapy or refractory to local therapy.
7. No evidence of uncontrolled hypertension as documented by 2 baseline blood pressure readings taken at least 1 hour apart. The baseline systolic blood pressure readings must be ≤ 140 mm Hg, and the baseline diastolic blood pressure readings must be ≤ 90 mm Hg. Patients whose hypertension is controlled by antihypertensive therapies are eligible.
8. Age ≥ 20 years.
9. ECOG performance status 0 or 1.
10. Estimated life expectancy of at least 3 months.
11. Required baseline laboratory data within the following parameters:
 - Neutrophils $\geq 1,500/\mu\text{L}$;
 - Platelets $\geq 75,000/\mu\text{L}$;
 - Hemoglobin ≥ 9.0 g/dL;
 - Serum aspartate aminotransferase (AST) and serum alanine aminotransferase (ALT) $\leq 5 \times \text{ULN}$;

- Estimated creatinine clearance ≥ 50 mL/min as calculated using the Cockcroft Gault (CG) equation;
 - INR < 1.7 or prothrombin time (PT) < 4 seconds above ULN (ie, Child-Pugh Score is no greater than 1);
 - Serum albumin ≥ 2.8 g/dL (ie, Child-Pugh Score is no greater than 2);
 - Total bilirubin ≤ 3 mg/dL (ie, Child-Pugh Score is no greater than 2);
 - Urinary protein $< 2+$ by urine dipstick. If dipstick is $\geq 2+$ then a 24 hour urine collection should be done and the patient may enter only if urinary protein is < 2.0 g per 24 hours.

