8.4.2. Potential Cases of Drug-Induced Liver Injury

Humans exposed to a drug who show no sign of liver injury (as determined by elevations in transaminases) are termed “tolerators,” while those who show transient liver injury, but adapt are termed “adaptors.” In some patients, transaminase elevations are a harbinger of a more serious potential outcome. These patients fail to adapt and therefore are “susceptible” to progressive and serious liver injury, commonly referred to as drug-induced liver injury (DILI). Patients who experience a transaminase elevation above 3 times the upper limit of normal (\times ULN) should be monitored more frequently to determine if they are an “adaptor” or are “susceptible.”

In the majority of DILI cases, elevations in aspartate aminotransferase (AST) and/or alanine aminotransferase (ALT) precede total bilirubin (TBili) elevations ($>2 \times$ ULN) by several days or weeks. The increase in TBili typically occurs while AST/ALT is/are still elevated above $3 \times$ ULN (ie, AST/ALT and TBili values will be elevated within the same lab sample). In rare instances, by the time TBili elevations are detected, AST/ALT values might have decreased. This occurrence is still regarded as a potential DILI. Therefore, abnormal elevations in either AST OR ALT in addition to TBili that meet the criteria outlined below are considered potential DILI (assessed per Hy’s law criteria) cases and should always be considered important medical events, even before all other possible causes of liver injury have been excluded.

The threshold of laboratory abnormalities for a potential DILI case depends on the patient’s individual baseline values and underlying conditions. Patients who present with the following laboratory abnormalities should be evaluated further as potential DILI (Hy’s law) cases to definitively determine the etiology of the abnormal laboratory values:

- Patients with AST/ALT and TBili baseline values within the normal range who subsequently present with AST OR ALT values $>3 \times$ ULN AND a TBili value $>2 \times$ ULN with no evidence of hemolysis and an alkaline phosphatase value $<2 \times$ ULN or not available;
- For patients with baseline AST **OR** ALT **OR** TBili values above the ULN, the following threshold values are used in the definition mentioned above, as needed, depending on which values are above the ULN at baseline:

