 - Preexisting AST or ALT baseline values above the normal range: AST or ALT values >2 times the baseline values AND $>3 \times$ ULN; or $>8 \times$ ULN (whichever is smaller).

- Preexisting values of TBili above the normal range: TBili level increased from baseline value by an amount of at least $1 \times \text{ULN}$ **or** if the value reaches $>3 \times \text{ULN}$ (whichever is smaller).

Rises in AST/ALT and TBili separated by more than a few weeks should be assessed individually based on clinical judgment; any case where uncertainty remains as to whether it represents a potential Hy's law case should be reviewed with the sponsor.

The patient should return to the investigator site and be evaluated as soon as possible, preferably within 48 hours from awareness of the abnormal results. This evaluation should include laboratory tests, detailed history, and physical assessment.

In addition to repeating measurements of AST and ALT and TBili, laboratory tests should include albumin, CK, direct and indirect bilirubin, GGT, PT/INR, total bile acids, alkaline phosphatase and acetaminophen drug and/or protein adduct levels. Consideration should also be given to drawing a separate tube of clotted blood and an anticoagulated tube of blood for further testing, as needed, for further contemporaneous analyses at the time of the recognized initial abnormalities to determine etiology. A detailed history, including relevant information, such as review of ethanol, acetaminophen (either by itself or as a coformulated product in prescription or over-the-counter medications), recreational drug, supplement (herbal) use and consumption, family history, sexual history, travel history, history of contact with a jaundiced person, surgery, blood transfusion, history of liver or allergic disease, and potential occupational exposure to chemicals, should be collected. Further testing for acute hepatitis A, B, C, D, and E infection and liver imaging (eg, biliary tract) may be warranted.

All cases demonstrated on repeat testing as meeting the laboratory criteria of AST/ALT and TBili elevation defined above should be considered potential DILI (Hy's law) cases if no other reason for the LFT abnormalities has yet been found. **Such potential DILI (Hy's law) cases are to be reported as SAEs, irrespective of availability of all the results of the investigations performed to determine etiology of the LFT abnormalities.**

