- Neutrophil count decreased:
 - derived absolute count does not meet Grade 2-4 criteria, and
 - % value < % LLN value, and
 - derived absolute count $\geq 1500/\text{mm}^3$.

For **calcium**, CTCAE grading is based on Corrected Calcium and Ionized Calcium (CALCIO). Corrected Calcium is calculated from Albumin and Calcium as follows:

- Corrected calcium (mmol/L) = measured total Calcium (mmol/L) + 0.02 (40 - serum albumin [g/L]).

Liver function tests: Alanine aminotransferase (ALT), aspartate aminotransferase (AST), total bilirubin (TBILI), and Alkaline Phosphatase (ALP) are used to assess possible drug induced liver toxicity. The ratios of test result over upper limit of normal (ULN) will be calculated and classified for these three parameters during the on-treatment period.

Summary of liver function tests will include the following categories. The number and percentage of patients with each of the following during the on-treatment period will be summarized by treatment group:

- ALT $\geq 3 \times \text{ULN}$, ALT $\geq 5 \times \text{ULN}$, ALT $\geq 10 \times \text{ULN}$, ALT $\geq 20 \times \text{ULN}$;

- $AST \geq 3 \times ULN$, $AST \geq 5 \times ULN$, $AST \geq 10 \times ULN$, $AST \geq 20 \times ULN$;
- $(ALT \text{ or } AST) \geq 3 \times ULN$, $(ALT \text{ or } AST) \geq 5 \times ULN$, $(ALT \text{ or } AST) \geq 10 \times ULN$, $(ALT \text{ or } AST) \geq 20 \times ULN$;
- $TBILI \geq 2 \times ULN$;
- Concurrent $ALT \geq 3 \times ULN$ and $TBILI \geq 2 \times ULN$;
- Concurrent $AST \geq 3 \times ULN$ and $TBILI \geq 2 \times ULN$;
- Concurrent $(ALT \text{ or } AST) \geq 3 \times ULN$ and $TBILI \geq 2 \times ULN$;
- Concurrent $(ALT \text{ or } AST) \geq 3 \times ULN$ and $TBILI \geq 2 \times ULN$ and $ALP > 2 \times ULN$;
- Concurrent $(ALT \text{ or } AST) \geq 3 \times ULN$ and $TBILI \geq 2 \times ULN$ and $(ALP \leq 2 \times ULN \text{ or } \text{missing})$.

Concurrent measurements are those occurring on the same date.

Categories will be cumulative, ie, a patient with an elevation of $AST \geq 10 \times ULN$ will also appear in the categories $\geq 5 \times ULN$ and $\geq 3 \times ULN$. Liver function elevation and possible Hy's Law cases will be summarized using frequency counts and percentages.

An evaluation of Drug-Induced Serious Hepatotoxicity (eDISH) plot will also be created, with different symbols for different treatment groups, by graphically displaying.

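### The SAP's possible Hy's Law count uses fixed 3×/2×ULN cut-offs, whereas the protocol's definition adjusts for raised baseline liver tests

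*SAP*

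**What the plan says.** **SAP 6.6.5.1 (liver function tests).** Possible Hy's "Law cases will be summarized using frequency counts and percentages". No table row carries that name. The combined rows pair ALT and/or AST ≥3×ULN with bilirubin ≥2×ULN, and two of them split further by ALP (above 2×ULN; at most 2×ULN or missing). The SAP adds: "Concurrent measurements are those occurring on the same date". Baseline enters none of these rows. The reference lines on the eDISH (drug-induced hepatotoxicity) plots use the same 3× and 2×ULN values.

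**Protocol 8.4.2.** "The threshold of laboratory abnormalities for a potential DILI case depends on" the patient's own baseline and underlying conditions. The 3×/2×ULN rule is given for "Patients with AST/ALT and TBili baseline values within the normal range who subsequently present with AST OR ALT values" above 3×ULN and bilirubin above 2×ULN. Where a baseline test is raised, other thresholds apply, "depending on which values are above the ULN at baseline":

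- AST/ALT: "AST or ALT values >2 times the baseline values AND" above 3×ULN, or above 8×ULN, whichever is smaller.
- Bilirubin: "TBili level increased from baseline value by an amount of at least" 1×ULN, or a value above 3×ULN, whichever is smaller.

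**Protocol 4.1, inclusion criterion 11.** AST and ALT may be up to 5×ULN at entry and total bilirubin up to 3 mg/dL.

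**The concern.** The two documents use the same name for different sets of patients. In advanced HCC many patients may enter with abnormal liver tests, and the eligibility limits allow it. A fixed multiple of ULN then cannot separate pre-existing liver disease from injury arising on treatment, which is the purpose of the protocol's baseline adjustment.

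Safety is the primary objective, so a table read as counting possible Hy's Law cases will carry weight. The count can also disagree with the SAE data, because potential cases are reported as SAEs under 8.4.2, and the SAP gives the reader no explanation for a difference.

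**Working it through.** The plan gives no figure for this count. Its one design figure, an 88% chance of seeing an AE of 10% incidence, reproduces (1 − 0.9^20 = 0.878), but nothing below depends on it.

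**Thresholds.** Let a be baseline AST (or ALT, each against its own baseline) and t baseline bilirubin, both in ×ULN.

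- SAP: 3 for AST/ALT and 2 for bilirubin, always.
- Protocol AST/ALT: 3 if a ≤ 1; otherwise min(max(2a, 3), 8).
- Protocol bilirubin: 2 if t ≤ 1; otherwise min(t + 1, 3).

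The differences between ≥ and >, and between ALP ≤2 and <2×ULN, are ignored as trivial.

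| Baseline AST or ALT | Protocol threshold (SAP: 3) | Rise needed, SAP | Rise needed, protocol |
|---|---|---|---|
| 1.5 | 3 | 1.5 | 1.5 |
| 2 | 4 | 1.0 | 2.0 |
| 2.5 | 5 | 0.5 | 2.5 |
| 3 | 6 | 0 | 3.0 |
| 4 | 8 | already 1.0 above | 4.0 |
| 5 | 8 | already 2.0 above | 3.0 |

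| Baseline bilirubin | Protocol threshold (SAP: 2) | Rise needed, SAP | Rise needed, protocol |
|---|---|---|---|
| 1.0 | 2 | 1.0 | 1.0 |
| 1.2 | 2.2 | 0.8 | 1.0 |
| 1.5 | 2.5 | 0.5 | 1.0 |
| 2.0 | 3 | 0 | 1.0 |
| 2.5 | 3 | already 0.5 above | 0.5 |

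**Direction.** min(max(2a, 3), 8) is never below 3, and min(t + 1, 3) exceeds 2 whenever t > 1. No same-date protocol case can therefore escape the SAP rows; the rows can only over-count. Every protocol case, simultaneous or not, also falls in the SAP listing, which is triggered by any one post-baseline value at a cut-off.

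**Example patients (×ULN).**

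| Baseline AST, bilirubin | On treatment | SAP | Protocol needs | Protocol |
|---|---|---|---|---|
| 3.2, 2.0 | 3.2, 2.0 (unchanged) | counted | AST >6.4, bilirubin 3.0 | not met |
| 2.5, 1.5 | 3.1, 2.1 | counted | AST >5, bilirubin 2.5 | not met |
| 2.5, 0.8 | 3.5, 2.1 | counted | AST >5, bilirubin >2 | not met |
| 0.9, 1.5 | 3.5, 2.2 | counted | AST >3, bilirubin 2.5 | not met |
| 2.5, 1.5 | 5.5, 2.6 | counted | AST >5, bilirubin 2.5 | met |

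**Can such patients be enrolled?** The documents give no bilirubin ULN. Assume 1.0, 1.2 or 1.5 mg/dL:

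- 1.5×ULN is 1.5, 1.8 or 2.25 mg/dL, and 2.0×ULN is 2.0, 2.4 or 3.0 mg/dL, all within the 3 mg/dL limit.
- 2.5×ULN is within the limit only if ULN is at most 1.2 (3/1.2 = 2.5).
- A value of 2 to 3 mg/dL scores 2 Child-Pugh points (protocol Appendix 2). Class A (5–6 points) then requires 1 point on each of the other four items: 2 + 4 = 6.

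**Size.** One patient in 20 is 5%, with an exact 95% interval of 0.1% to 24.9%.

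**The case against.** The strongest reply is that the two passages serve different purposes. Protocol 8.4.2 sits in the adverse event reporting section and tells investigators whom to evaluate and report. Protocol section 9 plans no Hy's Law count, 9.4.2 leaves other safety definitions to the SAP, and the SAP may modify the protocol. The SAP rows are titled by their numeric criteria, so none misstates its contents. Over-inclusion hides no signal. With about 20 patients, a reader could apply 8.4.2 by hand from the listing of all bilirubin, ALT, AST and ALP values.

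Much of this stands. The rows are a sensitive screen, and the listing, the eDISH plots, the CTCAE shift tables and the SAE listings are real safeguards. It is also true that a revised row need not agree with the SAE data, because 8.4.2 asks for confirmation on repeat testing and no other explanation, and SAEs are tabulated by organ class and preferred term.

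It does not remove the point. Section 8.4.2 is the only place where either document defines a potential Hy's Law case. The SAP promises a count under that name without saying that it departs from the definition or that its rows are only a screen. The safeguards leave the count unchanged: the eDISH lines are equally unadjusted, and the shift tables take one test at a time. With the grade limits in protocol Table 4, the patient moving from 2.5 and 1.5 to 3.1 and 2.1 appears there as two unrelated Grade 1 to 2 shifts.

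**Conclusion.** The concern holds. The SAP's possible Hy's Law count rests on criteria that ignore baseline, and it can include patients who do not meet the protocol's definition, even one whose values never moved. The discrepancy arises when baseline AST/ALT exceeds 1.5×ULN or baseline bilirubin exceeds ULN. On same-date values it is always an over-count.

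How many patients would be affected is unknown, because the documents give no baseline distribution of liver tests. The examples are illustrative, and those with raised bilirubin rest on the assumed ULN of 1.0 to 1.5 mg/dL. The consequence is limited to how liver safety is read: there is no hypothesis test or decision rule, and the primary laboratory endpoint is CTCAE-graded and reported in other tables. It is worth correcting because safety is the primary objective and the correction is cheap. The two passages need to be reconciled; nothing here says which threshold is clinically right.

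**What to change.** In SAP 6.6.5.1:

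1. Add one row, *potential Hy's law, laboratory criteria only*, derived from the protocol 8.4.2 thresholds: 3×/2×ULN where the baseline test is normal, the protocol's substituted threshold for each test that is not, and the protocol's ALP condition. State that AST and ALT are each compared with their own baseline.
2. Keep the existing rows, described as a biochemical screen that is not baseline-adjusted, and flag patients already at or above a cut-off at baseline.
3. Identify non-simultaneous rises, where the protocol regards AST/ALT having fallen before bilirubin rises as rare, from the existing eDISH plots and listing. A pre-specified pairing window is optional.

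The cost is SAP wording, one derivation, one table row and a flag. Baseline is already defined in SAP 3.4.1, and AST, ALT, bilirubin and ALP are core chemistry tests in protocol Table 5, so no new data are needed. The downside is two sets of rows to explain. A footnote should say that the new row may still differ from the SAE reports, because haemolysis, other causes and confirmation on repeat testing are not part of the derivation.

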3. ENDPOINTS AND BASELINE VARIABLES: DEFINITIONS AND CONVENTIONS

3.1. Primary Endpoints

- Adverse events (AEs) and laboratory abnormalities as graded by National Cancer Institute (NCI) Common Terminology Criteria for Adverse Events (CTCAE) v.4.03.

AEs will be graded by the investigator according to the CTCAE v.4.03 and coded using the Medical Dictionary for Regulatory Activities (MedDRA).

Laboratory abnormalities as characterized by type, severity (as graded by NCI-CTCAE v.4.03) and timing.

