3.5. Safety Endpoints

3.5.1. Adverse Events

Treatment-Emergent Adverse Events

Treatment-emergent adverse events (TEAEs) are those events with onset dates occurring during the on-treatment period for the first time, or if the worsening of an event is during the on-treatment period.

On-treatment period is defined as the time from the first dose of study treatment through minimum (30 days + last dose of study treatment, start day of new anti-cancer drug therapy – 1 day). The start day of new anti-cancer drug therapy after the first dose of study treatment is derived as outlined in [Section 5.2.5](#).

Adverse Events of Special Interest (AESIs)

AESIs are irAE and infusion-related reactions (IRRs). The criteria for classification of an AE as an irAE or IRR are described in [Appendix 1](#) and [Appendix 2](#), respectively.

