5. GENERAL METHODOLOGY AND CONVENTIONS

5.1. Hypotheses and Decision Rules

5.1.1. Hypotheses and Sample Size Determination

There is no formal hypothesis testing planned for this study.

This study will enroll 20 patients to evaluate overall safety and tolerability with combination of avelumab plus axitinib. A sample size of 20 patients will provide at least 88% probability to observe at least one AE if the true incidence of the AE in the population is 10% or more.

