- peak serum $ALT(/ULN)$ vs peak total bilirubin ($/ULN$) including reference lines at $ALT=3 \times ULN$ and total bilirubin $=2 \times ULN$.
- peak serum $AST(/ULN)$ vs peak total bilirubin ($/ULN$) including reference lines at $AST=3 \times ULN$ and total bilirubin $=2 \times ULN$.

In addition, a listing of all TBILI, ALT, AST and ALP values for patients with a post-baseline $TBILI \geq 2 \times ULN$, $ALT \geq 3 \times ULN$ or $AST \geq 3 \times ULN$ will be provided.

Parameters with NCI-CTC grades available:

The laboratory toxicities will be tabulated using descriptive statistics (number of patients and percentages) during the on-treatment period. The denominator to calculate percentages for each laboratory parameter is the number of patients evaluable for CTCAE grading (ie, those patients for whom a Grade 0, 1, 2, 3 or 4 can be derived).

- The summary of laboratory parameters by CTCAE grade table will include number and percentage of patients with Grade 1, 2, 3, 4, Grade 3/4 and any grade (Grades 1-4), laboratory abnormalities during the on-treatment period.

- The shift table will summarize baseline CTCAE grade versus the worst on-treatment CTCAE grade. The highest CTCAE grade during the on-treatment period is considered as the worst grade for the summary.

The above analyses apply to hematology and chemistry evaluations which can be graded per CTCAE, ie:

- Hematology:

Hemoglobin (HB), Leukocytes (white blood cell decreased), Lymphocytes (lymphocyte count increased/decreased), Neutrophils/Absolute Neutrophils Count (ANC) (neutrophil count decreased), Platelet Count (PLT) (platelet count decreased).

- Serum Chemistry:

Albumin (hypoalbuminemia), Alkaline Phosphatase (alkaline phosphatase increased), Alanine Aminotransferase (ALT) (ALT increased), Amylase (serum amylase increased), Aspartate Aminotransferase (AST) (AST increased), Total Bilirubin (blood bilirubin increased), Cholesterol (cholesterol high), Creatinine (creatinine increased), Creatine Kinase (CPK increased), Potassium (hypokalemia/hyperkalemia), Sodium (hyponatremia/hypernatremia), Magnesium (hypomagnesemia/hpermagnesemia), Calcium (hypocalcemia/hypercalcemia), Glucose (hypoglycemia/hyperglycemia), Gamma Glutamyl Transferase (GGT) (GGT increased), Lipase (lipase increased), Phosphates (hypophosphatemia), Triglycerides (hypertriglyceridemia).

Parameters with NCI-CTC grades not available:

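### SAP 6.6.5.1 counts graded laboratory abnormalities and liver multiples of ULN without regard to baseline, and its fixed Hy's Law cut-offs do not match protocol 8.4.2

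*SAP*

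**What the plan says.** Laboratory abnormalities are half of the primary endpoint. SAP 3.1 describes them thus: "Laboratory abnormalities as characterized by type, severity (as graded by NCI-CTCAE v.4.03) and timing". SAP 6.1.1.1 sends the primary analysis to Section 6.6.5 among others.

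SAP 6.6.5.1 plans these outputs for the tests at issue:

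- **By-grade frequency table.** Patients with Grade 1, 2, 3, 4, 3/4 and any grade on treatment, out of all patients whose grade can be derived. No baseline condition is stated.
- **Shift table.** Baseline grade against worst on-treatment grade, with the rule "The highest CTCAE grade during the on-treatment period is considered as the worst grade for the summary".
- **Liver table.** "Summary of liver function tests will include the following categories": ALT and AST at or above 3, 5, 10 and 20 x ULN, bilirubin at or above 2 x ULN, and same-date combinations with and without raised ALP. Possible Hy's Law cases are summarised as counts and percentages. No baseline condition is stated.
- **eDISH plots** of peak values, and a listing of all bilirubin, ALT, AST and ALP values for patients who cross the thresholds.

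Other parts of the plan do refer to baseline. Under SAP 3.5.1 an AE is treatment-emergent if it first occurs on treatment "or if the worsening of an event is during the on-treatment period". In SAP 6.6.5.1, tests without a CTCAE grade are counted only as shifts from a normal baseline. Protocol 8.4.2 makes the thresholds for a potential DILI case depend on the patient's baseline values.

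**The concern.** The study has one arm, so no control rate shows how many patients would have had the abnormality anyway. Protocol 1.2.1 says that most patients with HCC have underlying cirrhosis, and eligibility allows raised liver tests at entry. A patient whose values never move can therefore appear in a table of on-treatment abnormalities.

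The liver table matters most. Its concurrent rows are the ones a reader checks first for severe hepatotoxicity. A count there that includes unchanged entry values, under criteria different from those used for case reporting, could be read as a hepatic signal that the protocol's own definition would not call one.

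**Working it through.** **1. The plan's own figure.** SAP 5.1.1 gives n = 20 and "at least 88% probability to observe at least one AE if the true incidence of the AE in the population is 10% or more". Check: 1 - 0.9^20 = 0.878, which agrees after rounding. It concerns AEs, and nothing below changes it. With 20 evaluable patients, one patient is 1/20 = 5 percentage points.

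**2. Where entry values fall.** Inputs: protocol 4.1 item 11 and the hepatic bands in protocol Table 4 (Grade 2 is AST/ALT >3 to 5 x ULN or bilirubin >1.5 to 3 x ULN).

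- AST/ALT at entry may reach 5 x ULN, the top of Grade 2.
- Bilirubin at entry may reach 3 mg/dL. For an assumed ULN of 1.0 to 1.5 mg/dL this is 3/1.0 = 3.0 to 3/1.5 = 2.0 x ULN, within Grade 2.

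Pre-existing values can thus fill the Grade 1-2 and any-grade rows, AST/ALT >=3 x ULN and bilirubin >=2 x ULN. The AST/ALT Grade 3/4 row needs a rise above the entry limit.

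**3. What the shift table resolves.** The 3 and 5 x ULN cut-offs for AST/ALT practically coincide with grade boundaries, so the shift table shows baseline status there. The 2 x ULN cut-off for bilirubin lies inside the Grade 2 band, so a bilirubin shift table cannot show who was already above it. A shift table for single tests also cannot show who met a two-test combination at baseline.

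**4. A constructed patient.** AST 4 x ULN, bilirubin 2.5 mg/dL, ALP normal, every other Child-Pugh item 1 point, other criteria met, values unchanged on treatment. Assumed bilirubin ULN 1.25 mg/dL, so bilirubin is 2.5/1.25 = 2.0 x ULN.

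| Check | Requirement | Patient | Result |
|---|---|---|---|
| Eligibility (protocol 4.1, Appendix 2) | AST <=5 x ULN; bilirubin <=3 mg/dL; Child-Pugh A (5-6) | 4; 2.5; 1+1+1+2+1 = 6 | met |
| SAP concurrent row, ALP <=2 x ULN | AST >=3 and bilirubin >=2 x ULN, same date | 4 and 2.0 | counted |
| Protocol 8.4.2, AST | >2 x baseline (8 x ULN) and >3 x ULN, or >8 x ULN | 4 | not met |
| Protocol 8.4.2, bilirubin | rise of at least 1 x ULN (to 3.0), or >3 x ULN | 2.0 | not met |

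The SAP counts this patient and the protocol does not. The result holds for any ULN up to 1.25 mg/dL; at the 3 mg/dL entry limit the row can be reached for any ULN up to 1.5.

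**5. Direction of the mismatch.** With a raised baseline, the protocol's bilirubin threshold is the smaller of baseline + 1 x ULN and 3 x ULN. Baseline exceeds 1 x ULN, so this is always above 2 x ULN. Its AST/ALT threshold is never below 3 x ULN. On thresholds alone, the SAP rows can therefore only count more patients. The SAP's same-date rule can work the other way, because protocol 8.4.2 also accepts cases where AST/ALT has fallen by the time bilirubin rises.

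**6. Illustration for the any-grade row of one test.** Let b be the share with Grade 1 or higher at baseline that persists, and q the on-treatment incidence among patients at Grade 0. Both are assumptions. Row = b + (1-b)q; new cases = (1-b)q.

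| b | q | Row, of 20 | New, of 20 | Carried-over share |
|---|---|---|---|---|
| 0% | 10% | 2.0 | 2.0 | 0% |
| 30% | 10% | 7.4 | 1.4 | 81% |
| 60% | 10% | 12.8 | 0.8 | 94% |
| 80% | 10% | 16.4 | 0.4 | 98% |
| 30% | 30% | 10.2 | 4.2 | 59% |
| 60% | 30% | 14.4 | 2.4 | 83% |

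A new-or-worsened count would add patients who worsen from a non-zero grade. The carried-over share runs from 0% to 98%, so the documents do not fix it.

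**The case against.** The best reply is that the plan already compares with baseline. The shift table covers every graded test, protocol 9.4.1.2 puts shift tables in the primary safety analysis, and SAP 6.6.5.1 adds change from baseline by visit. A new-or-worsened count is the sum of the worsening cells of the shift table, and with about 20 patients nothing is lost. This largely stands for single graded tests, where the remaining gain is one of presentation.

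A further reply is that potential Hy's Law cases are identified under protocol 8.4.2 and reported as SAEs, and that the listing lets a reader trace each patient. Both are true, but neither corrects the counts in the concurrent rows.

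The consequence is also limited. SAP 5.1.1 states: "There is no formal hypothesis testing planned for this study". Under protocol 8.2.2, abnormal results that are symptomatic, need intervention or are judged to be AEs are recorded as AEs and fall under the treatment-emergent rule.

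A reader might infer that the laboratory half of the primary endpoint mostly measures underlying liver disease. The documents do not support that. They give no baseline prevalence; many graded tests (amylase, lipase, creatinine, creatine kinase, electrolytes, glucose, lipids) are not liver tests; and AST/ALT above Grade 2 is excluded at entry. Nor can the same argument be made from the documents for platelets or hemoglobin, whose CTCAE bands they do not print.

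**Conclusion.** The point holds in a limited form. The by-grade frequency table and the liver table take no account of baseline, unlike the AE rule and the ungraded tests. For single graded tests the planned shift table supplies the comparison. For bilirubin >=2 x ULN and the concurrent rows no table does, and the SAP's fixed cut-offs for possible Hy's Law cases disagree with protocol 8.4.2. That disagreement needs no assumption about prevalence; the worked patient needs only an assumed bilirubin ULN of 1.25 mg/dL or less.

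The overall size is unknown. Each affected patient adds 5 percentage points at n = 20, and more if fewer are evaluable. The illustrated shares rest on assumed b and q and on baseline grades persisting, and should not be quoted as estimates. The change is worth making because it is cheap and touches the liver rows of a single-arm safety study.

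**What to change.** In SAP 6.6.5.1:

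1. **Liver table.** Add a column for patients already in each category at baseline. Keep the fixed cut-off rows. Add a possible Hy's Law row programmed from the baseline-dependent laboratory criteria in protocol 8.4.2, and state how the same-date rule and the protocol's exclusion of hemolysis are handled, so that the two documents are reconciled.
2. **By-grade frequency table.** Keep the worst-grade counts, which follow protocol 9.4.1.2. Add a column for patients whose worst on-treatment grade exceeds their baseline grade. Report patients with a missing baseline separately; setting them to Grade 0 would count pre-existing abnormalities as new.

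The cost is a few extra columns and one row, programmed from baseline values and grades that the shift table and change-from-baseline summaries already need. No planned primary output is removed or redefined, so this should not count as a major modification needing a protocol amendment under protocol Section 9.
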